### 8.2.2. Data Analysis & Anticipated Results.

**Analysis of Primary Objective 1 and 2.** Examine the effects of oxytocin on the modified monetary and social incentive delay tasks.

*Analyses.* We will conduct whole-brain voxel-wise analyses with drug (Syntocinon® or Placebo) as a within-subject factor. We will examine the main effects of drug on reward related BOLD activity across the brain during both anticipation and outcome phases.

*Anticipated Results.* As oxytocin administration has been previously demonstrated to reduce amygdala activity in response to social challenges it is hypothesized that we will see a blunting of amygdala reactivity during the anticipation and attainment of social rewards (particularly for negative social incentives). Oxytocin has also been demonstrated to increase dopaminergic activity within the mesolimbic dopamine system (20) so we may see an enhancement of ventral striatal activity during the anticipation of social rewards; however, as Knutson and collaborators have reported that inducing dopamine release within the ventral striatum by amphetamine can actually reduce the difference in BOLD signal activity seen between the anticipation of reward and the anticipation of null (51), reductions in the BOLD response to anticipation of social reward within the ventral striatum is also possible.

While oxytocin has been predominately noted to affect social processes, there is some data to suggest that oxytocin's effects extend beyond modulating affiliative behaviors. Given this, we hypothesize oxytocin administration will show similar, though perhaps diminished, effects on amygdala and ventral striatal activity in response to the anticipation of monetary rewards as we see in anticipation of social rewards.

**Analysis of Primary Objective 3.** Compare responses to the modified monetary incentive delay task in participants with AUD versus controls.

*Analyses.* We will conduct whole-brain voxel-wise analyses with group (AUD or Control) as a within-subject factor. We will examine the main effects of group on reward related BOLD

activity across the brain during both anticipation and outcome phases.

*Anticipated Results.* It has been observed that individuals with AUD or with a family history of alcoholism show blunted NAc activity during the anticipation of non-drug rewards which may reflect a bias towards alcohol related stimuli. Both the insula and ACING are also implicated in the neurobiology of AUD. Indeed, lower insular activity has been demonstrated to be predictive of relapse and ACING responsivity to the anticipation of monetary reward is inversely related to characteristics associated with AUD including impulsivity. Hence, we expect to observe lower BOLD responses to the anticipation of rewards within the NAc, insula and ACING, in the AUD group compared to controls.

**Analysis of Primary Objective 4.** Compare the effects of oxytocin on the modified monetary incentive delay task in participants with AUD versus controls.

*Analyses.* We will conduct whole-brain voxel-wise analyses with drug (Syntocinon® or Placebo) and group (AUD or Control) as within-subject factors. We will examine the main effects of drug on reward related BOLD activity across the brain during both anticipation and outcome phases and compare this activity between groups.

*Anticipated Results.* We expect the oxytocin intervention to have a larger effect on BOLD responses to the anticipation of social rewards on individuals with AUD for several reasons. First, it is hypothesized that individuals with social impairments, which are common in persons diagnosed with substance dependence, may receive greater benefit from exogenous oxytocin. Second, it is proposed that circulating levels of oxytocin may moderate how a given individual response to exogenous administration of oxytocin. Lower plasma oxytocin levels have been noted in individuals with substance dependence and morphological abnormalities have been noted in the oxytocinergic neurons of individuals with AUD. Finally, though oxytocin is known to impact social reward processing, it also may influence reward activity more generally. To explore the selectivity of oxytocin's effects, I will analyze anticipatory reward activity in regions identified as significant in the group analyses above and compare SID and MID activity. While we expect specific effects of oxytocin on the SID, if oxytocin was shown to influence reward activity irrespective of social content, this would indicate an exciting, broad role of oxytocin in reward in AUD. This would be of great interest to those seeking to utilize oxytocin to treat AUD, where reward dysfunction is known to play a key role.

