## **3. STUDY DESIGN**

This is a double-blind, placebo-controlled, randomized study of the effects of Syntocinon® on brain activity elicited during the processing of reward. Each participant will be studied twice using fMRI; once self-administering Syntocinon® and once self-administering placebo intranasally approximately 30 minutes prior to being scanned. Participants will be randomly assigned to self-administer either Syntocinon® or placebo first. Scans will be performed on separate days approximately 1-2 weeks apart.

Participants will be evaluated thoroughly at screening for eligibility and will only be entered into the study if they meet all inclusion criteria and none of the exclusion criteria.

88 participants are planned to complete the study (44 controls, 44 AUD). Total duration of the study is expected to be 60 months.

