## 5. STUDY TREATMENTS

### 5.1. Allocation to Treatment

Eligible participants will be randomly assigned to administer either Syntocinon® or placebo first, prior to scanning using a computer-generated randomization scheme. Neither the research staff, nor the participants will know the identity of the test and control drugs. On behalf of PharmaWorld, Volkapotheke Roten Ochsен will transfer Syntocinon® into bottles identical to placebo using sterile procedures. To maintain the blind, packaging and labeling of test and control treatments will be identical to maintain the blind.

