### **6.6. Scanning Session 2**

1. Review procedure with participant, noting any changes in health (such as nasal congestion or upper-respiratory issues) prior to drug administration.
2. Collect urine for drug screen and perform urine drug analysis to ensure no acute drug use. Record blood pressure and heart rate. Ask participant to give a saliva sample for laboratory testing.
3. Participant will practice the fMRI tasks on a laptop to remind them how to perform each of the tasks.
4. Participant will self-administer either placebo or Syntocinon® (blinded to both research staff and participant) over 5 minutes.
5. Record and respond to any adverse experiences. Record blood pressure and heart rate.
6. Ask participant to complete several measures designed to assess mood, social perception, and anxiety while waiting for scanning.
7. Participant will be placed into the scanner and scanned under several conditions which may include:
  - a. Preliminary scans including collection of anatomical overlay
  - b. SID task
  - c. MID task
  - d. Hemodynamic Response Function
  - e. Why/How / Photography Judgement Task
  - f. Anatomical/connectivity images
8. Ask participant to complete the delayed discounting, time perception, and FERT.
9. Ask participant to complete measures designed to assess mood, social perception and anxiety (see section 6.10)
10. Ask participant to rate faces (e.g. trustworthiness) that may have been given as part of the SID task. Record blood pressure and heart rate. Ask participant to give a saliva sample for laboratory testing.
11. Any adverse events will be recorded and information for the next scanning session will

be provided. Participants will be asked questions regarding their scanning experience and to guess whether they received oxytocin or placebo during each scan. A phone number will be collected so the participant can be contacted the next day to follow-up on any potential effects.

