## 8.2. Analysis of Primary Endpoint

### 8.2.1. fMRI Data Processing.

**Preliminary processing.** All fMRI data will be submitted to an initial series of preprocessing steps (e.g. slice-timing correction, realignment, artifact checks). The functional data acquired for each subject will be coregistered to the structural image collected and finally warped into standardized space using specialized neuroimaging software (e.g. Statistical Parametric Mapping software [SPM8, Wellcome Department of Cognitive Neurology, University College, London, UK]).

**Subject-level analysis.** For each task (for both Syntocinon® and Placebo conditions), a general linear model will be constructed with parameters corresponding to the anticipation and outcome of each type of reward at stake, modeling each session separately. Each stimulus type will be convolved with the hemodynamic response function to assess task-related changes in BOLD signal. Contrasts will be constructed to test for BOLD differences in anticipation activity (anticipation of reward vs null) and outcome activity (outcomes for reward trials versus outcomes for null trials) for each reward type. The statistical maps generated by these analyses will then be slightly smoothed and introduced into second level-analyses.

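### The second-level crossover models in 8.2.2 name drug, or drug and group, but no session term; the precision loss falls mainly on the drug-by-group comparison

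*Protocol*

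**What the plan says.** - **Design.** Protocol 3 describes two scans per participant with the order of oxytocin and placebo randomised: "Scans will be performed on separate days approximately 1-2 weeks apart". It plans 88 completers, 44 per group.
- **Model, Objectives 1 and 2 (8.2.2).** "We will conduct whole-brain voxel-wise analyses with drug" as a within-subject factor. The effect tested is the drug main effect: "We will examine the main effects of drug on reward related BOLD activity across the brain during both anticipation and outcome phases".
- **Model, Objective 4 (8.2.2).** Drug "and group (AUD or Control) as within-subject factors". Group is in fact a between-subject factor. That mislabel is a separate matter.
- **First level (8.2.1).** The per-subject models are fitted "modeling each session separately".
- **Covariates (8.2.3).** Age is the named example, with attachment and sociability measures. Session and order are not mentioned.
- **Task lists (6.4 and 6.6).** Session 1 lists the monetary task (MID) before the social task (SID); session 2 lists SID before MID. Both lists have the same lead-in: "scanned under several conditions which may include".
- **Randomisation (5.1).** Drug order is assigned "prior to scanning using a computer-generated randomization scheme". Blocking and stratification are neither stated nor excluded.

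**The concern.** In a two-session crossover, the oxytocin-minus-placebo difference of one participant contains the drug effect plus or minus any change from first to second scan. The sign depends on which drug came first. Practice or reduced novelty could cause such a change. So could a different task position or time since dosing, if the listed orders are followed. Protocol 6.3.2 times scanning to peak oxytocin levels, so the protocol itself treats time since dosing as relevant.

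Fitting each session separately at the first level does not remove this shift, because the shift is still in the contrast maps carried to the second level. There, a model with drug alone treats it as residual noise. Two things are at stake: precision of the drug and drug-by-group tests and, when the order split differs between groups, the realised drug-by-group estimate.

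**Working it through.** **Inputs from the protocol (8.1 and 3).** 44 per group; one-sided 0.005; d = 0.77; stated power at least 90% with 44 subjects. The protocol does not say which contrast 0.77 refers to. Here it is applied, as an assumption, to the within-person drug difference and to its difference between groups.

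**The plan's own figure.** Noncentral t power at d = 0.77:
- Paired, n = 44: noncentrality 0.77 × √44 = 5.11, 43 df, power 99.0%. This is consistent with at least 90%.
- Two groups of 44: noncentrality 0.77 × √22 = 3.61, 86 df, power 83.3%. This is below 90%.

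The drug-by-group test thus has less room than the paired test before any session effect is considered.

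**Model for the shift.** For one participant, D = δ + sπ + e. Here s = +1 if oxytocin is given in session 2 and −1 if in session 1, SD(e) = 1, and π is the session-2-minus-session-1 shift in SDs of the within-person difference. The documents give no value for π, so a range is shown.

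**Precision, balanced sequences (22/22 in each group).** Leaving session out multiplies the variance used for the test by 1 + π². Power at d = 0.77 by simulation (40,000 replicates):

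| π (assumed) | 1 + π² | Paired drug effect, n = 44 | Drug by group, 44 v 44 |
|---|---|---|---|
| 0 | 1.00 | 98.9% | 83.5% |
| 0.25 | 1.06 | 98.7% | 81.2% |
| 0.5 | 1.25 | 97.7% | 74.4% |
| 0.75 | 1.56 | 95.1% | 61.9% |

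With the session term, paired power stays at 98.9% at every π. For drug by group, the residual variance returns to 1 and 86 df become 85 or 84. The noncentrality is still 3.61, so power is again about 83%.

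**Bias in the realised drug-by-group estimate.** Let kA and kC be the numbers in the AUD and control groups given oxytocin in session 2. Then bias = π × 2(kA − kC)/44, which is zero when the splits are equal. At π = 0.5:

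| Split (AUD v control) | Bias | One-sided rejection under the null, given this split |
|---|---|---|
| 24 v 20 | 0.5 × 2 × 4/44 = 0.09 SD | 0.7% |
| 26 v 18 | 0.5 × 2 × 8/44 = 0.18 SD | 2.2% |
| 28 v 16 | 0.5 × 2 × 12/44 = 0.27 SD | 5.3% |

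The nominal rate is 0.5%. For scale, the standard error of the group contrast without a session shift is √(2/44) = 0.21 SD.

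If order were assigned by simple randomisation, which is an assumption, the two counts would differ by 4 or more with probability 46%, by 8 or more with 11% and by 12 or more with 1.4%. Averaged over such randomisations, simulated type I error is 0.46%, 0.51% and 0.50% at π = 0.25, 0.5 and 0.75.

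**The case against.** - **The text does not exclude a session term.** Drug is called a within-subject factor, not the only one, and a statistical analysis plan that is not at hand could add session. That is fair. Still, the protocol goes beyond silence: it names the factors for each primary objective and the covariates for adjustment, and session is in neither list.
- **The drug main effect is hardly touched.** This stands. At the planned d = 0.77 the paired test stays at 95% or above over the assumed range with balanced sequences. A much larger loss can be shown by substituting a smaller effect: at d = 0.60, power goes from 89.6% to 72.1% at a 0.75 SD shift. The protocol does not plan on that effect.
- **A session shift may be small.** The contrasts are reward versus null within the same task and session, so shifts common to both conditions cancel. Tasks are practised before each scan, and target timing is adjusted to about 66% success. These features limit the shift but do not make it zero, and the 0.5 and 0.75 SD values have no support in the documents.
- **Task reversal.** A reader might infer that the protocol fixes a reversed task order and so builds in a session effect. The lists say what the scan may include, and no sentence states an acquisition order. The reversal is suggested, not fixed. Task durations are not given, so the change in time since dosing cannot be sized.
- **Randomisation.** A reader might infer that drug order is unstratified and that this is an error. Section 5.1 does not describe the scheme in that detail, so no error is shown.
- **False positives.** A reader might infer an inflated type I error for Objective 4. Over randomisations it stays nominal; only the estimate from an unequally split trial is biased.

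**Conclusion.** The concern holds as a concrete, nearly free improvement to the stated second-level models. With balanced sequences the omission does not bias the drug effect; it costs precision. At d = 0.77 the cost is minor for the drug main effect and material for drug by group, where power falls from 83% to about 74% at an assumed 0.5 SD shift. Bias in the realised drug-by-group estimate needs both a session shift and a chance difference in order split between AUD and controls.

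These sizes rest on the assumed shift, on applying d = 0.77 to both contrasts and, for the probabilities of unequal splits only, on simple randomisation.

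**What to change.** In 8.2.2, add session (first or second) as a within-subject term in every second-level drug and drug-by-group model; equivalently, adjust the within-person drug difference for sequence. Do the same in the region-of-interest analyses of 8.2.3. Allow a session-by-group term if the shift may differ between AUD and controls, because a common session term would not remove such a difference. Make the change before unblinding, so that it cannot look data-driven.

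The cost is one degree of freedom, or two with session-by-group. No new data are needed, because session number is known for every scan.

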### **Objectives and Endpoints**

Our primary objectives: examine the effects intranasal oxytocin administration has on brain activity elicited by social and monetary incentives using incentive delay tasks, which are designed to engage circuits that process natural and artificial rewards, in a group of healthy participants and participants diagnosed with AUD. This will allow us to establish whether intranasal oxytocin can influence brain activity associated with the processing of rewards and given the social nature of the hormone, whether oxytocin can influence such reward-related activity in a general sense or only when the reward has direct social relevance, and whether oxytocin produces similar alterations to reward-related activity in individuals diagnosed with AUD. Our study end will correspond to the final scan follow-up of our final participant.

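### The protocol promises to separate a general from a social-only oxytocin effect on reward, but Objectives 1 and 2 state no drug-by-task contrast and the only SID–MID comparison is exploratory

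*Protocol*

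**What the plan says.** - **The question.** Protocol Summary, Objectives and Endpoints: the study will establish "whether oxytocin can influence such reward-related activity in a general sense or only when the reward has direct social relevance".
- **The listed objectives.** Section 2.1.1 has one objective for social reward and a separate one for monetary reward. None is phrased as a difference between them.
- **First-level contrasts.** Section 8.2.1 builds reward-against-null contrasts, including "outcome activity (outcomes for reward trials versus outcomes for null trials) for each reward type". It names no SID-minus-MID contrast.
- **Group analysis for Objectives 1 and 2.** Section 8.2.2: "We will conduct whole-brain voxel-wise analyses with drug" as a within-subject factor, and then "We will examine the main effects of drug on reward related BOLD activity across the brain during both anticipation and outcome phases". Task is not named as a factor.
- **Prediction under Objectives 1 and 2.** "similar, though perhaps diminished, effects on amygdala and ventral striatal activity in response to the anticipation of monetary rewards", relative to social reward.
- **The one SID–MID comparison.** Under the anticipated results for Objective 4, to explore selectivity: "I will analyze anticipatory reward activity in regions identified as significant in the group analyses above and compare SID and MID activity".
- **Prediction attached to it.** "While we expect specific effects of oxytocin on the SID", with a broader role in reward in AUD as the alternative.

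**The concern.** Whether oxytocin acts on reward in general or only on social reward depends on how the drug effect in SID compares with the drug effect in MID. A main effect of drug, whether pooled over tasks or examined within each, does not test that. With no stated contrast between the two drug effects, the natural reading of the results is to note where SID reaches significance and MID does not. That pattern is weak evidence of a difference: two equal effects can fall on opposite sides of a threshold, and a smaller but real monetary effect can miss it.

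The comparison under Objective 4 does not fill the gap. It covers anticipation only, while the Objectives 1 and 2 analysis covers outcome as well. It runs only where an effect was already significant, which favours whichever task drove the selection. It speaks of comparing activity and does not say that oxytocin-minus-placebo differences are what is compared.

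The two predictions add to the difficulty. One expects similar, perhaps weaker, effects for money; the other expects effects specific to SID. Unless they are meant for different groups, either result could be reported as predicted.

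**Working it through.** **Inputs from the protocol.** One-sided threshold 0.005, n = 44 and effect 0.77 SD (Section 8.1); 88 planned completers, 44 per group (Section 3).

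**Assumptions, not in the protocol.** The drug effect in each task (d from 0.3 to 0.77) and the within-person correlation ρ between the two drug effects (0 to 0.7).

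**1. The plan's own figure.** Section 8.1 states at least 90% power at d = 0.77 with 44 subjects. For a paired test, power = P(T > t₀.₉₉₅,₄₃), where T is noncentral t with noncentrality d√n = 0.77 × √44 = 5.11 and the critical value is 2.695. This gives 99.0%. A two-sample test of 44 against 44 gives 83.3%. Section 8.1 does not say which test the figure belongs to, and the inputs to the power software are not shown, so the mismatch proves no error. It does not decide this point. No power is stated for a SID–MID contrast.

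**2. Equal true effects: how often is SID significant and MID not?** When ρ = 0 the probability is p(1 − p), with p the power of one task's test. At n = 44:
- d = 0.3: 0.254 × 0.746 = 0.19
- d = 0.4: 0.490 × 0.510 = 0.25
- d = 0.5: 0.730 × 0.270 = 0.20
- d = 0.77: 0.990 × 0.010 = 0.01

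For ρ > 0, simulation with 40,000 trials per scenario gives the SID-only share:

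| n | d | ρ = 0 | ρ = 0.3 | ρ = 0.5 | ρ = 0.7 |
|---|---|---|---|---|---|
| 44 | 0.3 | 18.6% | 16.0% | 13.4% | 10.4% |
| 44 | 0.4 | 24.9% | 20.5% | 16.8% | 13.3% |
| 44 | 0.5 | 19.8% | 16.7% | 13.8% | 10.6% |
| 44 | 0.77 | 0.9% | 0.9% | 0.9% | 0.7% |
| 88 | 0.3 | 24.5% | 20.1% | 16.6% | 12.8% |
| 88 | 0.4 | 11.8% | 9.9% | 8.7% | 6.6% |
| 88 | 0.5 | 2.1% | 2.0% | 1.9% | 1.4% |

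In the same simulations a direct test of the difference between the two drug effects is falsely significant in about 0.5% of trials.

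**3. Monetary effect half the social one.** Section 8.2.2 allows for a diminished monetary effect; the ratio of one half (0.77 and 0.385) is assumed. At n = 44 the two powers are 0.990 and 0.452, so at ρ = 0 the SID-only share is 0.990 × (1 − 0.452) = 0.54. At n = 88 it is 1.00 × (1 − 0.833) = 0.167. The simulation gives 54% at n = 44 and 16–17% at n = 88 for every ρ tried. Oxytocin acts on both rewards in all of these trials.

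**4. What the direct contrast can detect.** Its standardised effect is (d_SID − d_MID)/√(2(1 − ρ)).
- 0.77 against 0.385: 0.385/√2 = 0.272 at ρ = 0, and 0.385/√0.6 = 0.497 at ρ = 0.7. Power is 20% to 72% at n = 44, and 47% to 98% at n = 88.
- 0.77 against 0 (wholly social): power is 82% to over 99% at n = 44.

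**The case against.** **A SID–MID comparison is planned.** This stands. A reader might infer that the protocol has no such comparison, or that it will declare social specificity whenever only SID is significant. The documents support neither: the comparison is there under Objective 4, and no sentence states that decision rule. What can be said is that the comparison is exploratory, restricted in phase and region, and imprecisely worded, so the misreading is left open.

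**The formal objectives do not ask for a difference.** True of Section 2.1.1. But the summary ties the general-or-social question to the primary objectives, and the stated analysis does not answer it.

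**Full factor structures belong in an analysis plan.** In part. Section 8.2.2 does, however, name both the factor and the effect to be tested, and these do not match the question in the summary. The per-task contrasts of Section 8.2.1 make the missing contrast easy to form.

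**The predictions may concern different groups.** Possible, since the second sits under the AUD-versus-control objective. A reader might infer an outright contradiction; the placement does not establish one. The protocol should say which is meant.

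**The size depends on assumptions.** It does. At 0.77 in both tasks the false pattern occurs in about 1% of trials, and with 88 subjects it is about 2% at d = 0.5. Section 8.2.2 does not limit Objectives 1 and 2 to one group. However, Section 8.1 does not say that 0.77 is a drug effect or that it holds in each task, and the precedent it cites is for task effects. The calculation also applies the region-of-interest threshold of Section 8.1, not a whole-brain criterion.

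**An interaction test does not settle general versus social-only.** Correct. Significance shows that the effects differ, not that the monetary effect is absent; non-significance does not show generality. The fix is framed accordingly.

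**Conclusion.** The concern holds in limited form. The summary poses a question about the difference between two drug effects; the analysis stated for Objectives 1 and 2 tests main effects of drug; and the one comparison of the tasks is too restricted and too loosely worded to serve as the answer. The resulting risk ranges from negligible to serious. With equal effects at n = 44 it is about 13–25% for d = 0.3–0.4 (ρ from 0.5 to 0) and about 1% for d = 0.77. With a monetary effect half the social one it is about 54% at n = 44 and 16–17% at n = 88. These figures rest on assumed per-task effects and correlations, on a one-sided 0.005 test in a single region, and on a reading of the results that the protocol leaves open but does not prescribe. The change is worth making because it needs no new data.

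**What to change.** In Section 8.2.2, Objectives 1 and 2:

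1. Add task (SID, MID) as a second within-subject factor.
2. State the drug-by-task contrast, (oxytocin minus placebo in SID) minus (oxytocin minus placebo in MID), in the regions already named in Section 8.2.3 (ventral striatum, amygdala, thalamus), for both anticipation and outcome, and not only in regions selected for significance.
3. State the permitted conclusions. Claim a larger effect for social reward only if this contrast is significant. Before saying social only, report the monetary drug effect with its confidence interval. Do not take a non-significant contrast as proof of a general effect.
4. Say whether the predictions under Objectives 1 and 2 and under Objective 4 apply to different groups; if not, reconcile them.

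Cost: wording and analysis only, on the same scans. The contrast can have less power than each task's own test (about 20–72% at n = 44 for 0.77 against 0.385, ρ from 0 to 0.7), so a specificity claim becomes harder to make.

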#### **2.1.1. Primary Objectives**

- To determine the effect of intranasal oxytocin (Syntocinon®) on brain activity associated with social rewards using fMRI.
- To assess the effects of intranasal oxytocin (Syntocinon®) on the neural processing of non-social (i.e. monetary) rewards.
- To determine whether the neural responses to social cues and rewards are altered in recently abstinent persons with AUD.
- To determine whether the effect of intranasal oxytocin (Syntocinon®) on brain activity associated with social cues and rewards differs between control participants and recently abstinent persons with AUD.

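### Primary Objectives 3 and 4 ask about social reward in AUD, but their analysis statements in section 8.2.2 name only the monetary task

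*Protocol*

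**What the plan says.** The protocol describes the scope of the AUD questions in three places, and the three differ.

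- **Protocol Summary, Objectives and Endpoints.** The primary aim is the oxytocin effect on "brain activity elicited by social and monetary incentives using incentive delay tasks", in healthy participants and in participants with AUD. Both reward types are in scope.
- **Section 2.1.1.** Objective 3 is "To determine whether the neural responses to social cues and rewards are altered in recently abstinent persons with AUD". Objective 4 asks whether the oxytocin effect "on brain activity associated with social cues and rewards differs between control participants and recently abstinent persons with AUD". Objective 2 concerns oxytocin effects "on the neural processing of non-social (i.e. monetary) rewards", so the protocol's own label for monetary reward is non-social.
- **Section 8.2.2.** The statement for Objectives 1 and 2 is "Examine the effects of oxytocin on the modified monetary and social incentive delay tasks". For Objective 3 it is "Compare responses to the modified monetary incentive delay task in participants with AUD versus controls". For Objective 4 it is "Compare the effects of oxytocin on the modified monetary incentive delay task in participants with AUD versus controls".

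Section 6.3.2.1 defines the MID as the monetary task and the SID as the one with social feedback. Sections 6.4 and 6.6 list them as separate scan items at both sessions.

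**The concern.** Read literally, section 8.2.2 places the AUD-versus-control comparison and the comparison of oxytocin effects between groups on the reward that Objective 2 calls non-social. A result on the MID would not by itself answer a question about social reward. Section 6.3.2.1 says as much, citing earlier work in which the brain's response to social incentives differed from its response to money alone.

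This is more than detail that could wait for an analysis plan. The protocol names a task, and the task does not match the objective, so a later plan would have to depart from one section or the other. Until that is settled, either task could be presented as the answer to Objectives 3 and 4, and the choice could be made after both sets of maps have been seen.

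**Working it through.** No arithmetic applies. The check sets each objective beside its analysis statement and then looks for other text that might close the gap.

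| Objective (2.1.1) | Reward type in the objective | Task named in the 8.2.2 statement |
|---|---|---|
| 1 | social | monetary and social (shared statement) |
| 2 | monetary, labelled non-social | monetary and social (shared statement) |
| 3 | social | monetary only |
| 4 | social | monetary only |

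**Step 1: is the monetary task name an umbrella term?** Section 6.3.2.1 introduces the SID as part of an adapted incentive delay paradigm, so the name could in principle cover both. Section 8.2.2 does not use it that way. It lists the two tasks separately for Objectives 1 and 2 and later contrasts SID with MID activity under Objective 4. With that usage, leaving out the social task for Objectives 3 and 4 changes the meaning.

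**Step 2: does the rest of the Objective 3 text bring the SID in?** Its analysis paragraph refers to reward-related activity in the anticipation and outcome phases and names no task. Its anticipated results discuss non-drug rewards and give one monetary example. The prediction is "lower BOLD responses to the anticipation of rewards within the NAc, insula and ACING, in the AUD group compared to controls". Neither the SID nor social reward appears.

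**Step 3: does the rest of the Objective 4 text bring the SID in?** Partly. Its anticipated results predict a larger oxytocin effect on anticipation of social reward in AUD and expect effects specific to the SID. The one analytic step that names the SID is an SID-versus-MID comparison. That step is described as exploring selectivity, covers anticipation only, and is limited to regions already found significant. It is not a stated drug-by-group analysis of the SID.

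**Step 4: does section 8.2.1 bring the SID in?** It builds anticipation and outcome contrasts for each reward type and passes the resulting maps to second-level analysis. SID maps are therefore available at group level, but no sentence assigns them to Objective 3 or 4.

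**The case against.** The strongest reply is that the mismatch lies in two one-line statements and that the surrounding text shows what was meant. The analysis paragraphs under Objectives 3 and 4 speak of reward-related activity without restricting the task, section 8.2.1 sends maps for every reward type forward, and the Objective 4 prediction is about social reward. This stands in part. It makes a drafting slip the likely explanation, and it makes the SID intent for Objective 4 partly recoverable. It does not help Objective 3, where nothing points to the SID.

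A second reply concerns grammar. In Objectives 3 and 4 the word social might qualify only cues, leaving rewards general. Section 6.3.2.1 does use social cues to describe a different task (Why-How), and section 1.2.1 states the AUD aim as reward-related activity. On that reading the monetary task is relevant but incomplete: general reward still includes social reward, and the social-cue part would still have no analysis named in section 8.2.2. The text needs correcting on either reading.

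Two stronger inferences should be resisted. A reader might conclude that the social AUD questions will go untested. The documents do not support that, because the SID is scanned at both sessions, modelled at subject level and carried into second-level analysis. A reader might also notice that the region list in section 8.2.3 does not name the insula or ACING and infer that the Objective 3 prediction would be missed. That does not follow either: the Objective 3 analysis is whole-brain, and the region list is an additional strategy that is not worded as exhaustive.

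**Conclusion.** The point holds as an inconsistency between objectives and analysis statements. It affects two of the four primary objectives: clearly for Objective 3, partially for Objective 4. The conclusion rests on the protocol's own classification of monetary reward as non-social and on its separate use of MID and SID within section 8.2.2.

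It should be fixed, but it does not call the design, sample size, data collection or safety of the trial into question. Confidence is high that the wording conflicts. The documents do not settle which side was intended, although the Objective 4 prediction favours the social task.

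**What to change.** In section 8.2.2, name the SID anticipation and outcome contrasts as the group analysis for Objective 3 and as the drug-by-group analysis for Objective 4. If the MID is also intended, list it beside the SID and say which task answers the objective. If the monetary task was what the investigators meant, reword Objectives 3 and 4 in section 2.1.1 instead. In either case, bring the Protocol Summary into line.

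The cost is a protocol amendment, with the IRB review that section 11.1 requires. No new scans or subject-level models are needed. Adding the SID beside the MID brings extra group-level comparisons, which is a small price; replacing the MID brings none. Section 2.2.1 defers all group-level analyses until the last participant's final scan follow-up, so the change should be made before then.
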